Research Question

How do different ketone supplement types affect blood beta-hydroxybutyrate $(\beta\text{-OHB})$ and blood glucose in healthy individuals?

Objectives

- a) To determine the effect of acute ketone supplementation on blood β -OHB across different types of ketone supplements.
- b) To compare changes in blood glucose following acute supplementation with different types of ketone supplements.
- c) To evaluate the influence of acute ketone supplementation on blood pressure and heart rate across different types of ketone supplements.
- d) To investigate the effect of acute supplementation with different ketone supplements on gastrointestinal discomfort, hunger, and fullness.
- e) To explore supplement acceptability and taste across different ketone supplements.

Hypotheses

- a) All ketone supplements will raise blood β -OHB.
- b) All ketone supplements will lower blood glucose.

This is an exploratory/descriptive pilot study that is designed to inform future research; therefore, we do not pose specific hypotheses as to how the ketone supplements will differ with respect to their effects on the above-outlined objectives.

Background Information

Acute increases in blood ketones (beta-hydroxybutyrate, β -OHB) have been found to temporarily reduce blood glucose [1] but therapeutic application has traditionally been limited due to the need for ketone infusion or severe dietary restrictions to achieve nutritional ketosis. With the recent development of exogenous ketone supplements that can be consumed orally [2], it is now possible to acutely raise blood β -OHB concentration without the need for other nutritional modifications or invasive procedures. In our lab, we have previously shown that acute ingestion of oral ketone supplements potently increases β -OHB and immediately lowers blood glucose [3-6]. These findings suggest exogenous ketones to be a promising therapeutic strategy aimed at lowering blood glucose and improving blood glucose control in individuals with impaired glucose metabolism, particularly individuals with prediabetes or type 2 diabetes [7].

The first ketone supplements available on the market were in the form of either ketone salts (i.e., β -OHB bound to a mineral salt) or ketone monoesters (i.e., β -OHB bound to a ketone precursor such as butanediol) [2]. Ketone salts can lead to gastrointestinal discomfort in many individuals [8] and ketone monoesters have an extremely unpleasant bitter taste. This makes adherence to a nutritional supplement regimen using ketone salts or monoesters challenging. Since then, new formulations have been developed that differ with respect to ingredients (e.g., include flavouring to mask the bitter taste and improve palatability) and chemical properties (e.g., different precursors and/or types of molecule the β -OHB is bound to). In particular, two new ketone supplements (beta-hydroxybutyric acid and 1,3-Butanediol) have recently become commercially available that promise an improved consumer experience.

However, little is known about the pharmacokinetics of these supplements, which can be expected to differ from the original supplements based on differences in formulation. This, in turn, may affect the glucose-lowering properties of the exogenous ketone supplements. While qualities such as an improved taste and gastrointestinal tolerability are desirable in ketone supplements, it is of importance for the field of research focusing on the therapeutic value of exogenous ketones to establish the effect of these different ketone supplements on blood β -OHB and blood glucose and determine how they compare to the effects of the by now well-established ketone monoester.

The overall aim of this pilot study is therefore to test the β -OHB-raising and glucose-lowering effect of these two new types of commercially-available oral ketone supplements (beta-hydroxybutyric acid and 1,3-Butanediol) in comparison to a ketone monoester, which we have used in our previous studies on ketone supplementation.

Research Method

Experimental design

A double-blind randomized cross-over pilot study in which N = 12 healthy adults will participate in three experimental trials with a different ketone supplement in each trial. Each ketone supplement has FDA GRAS (Generally Recognized As Safe) status as a food additive and is available for online purchase in Canada:

- 1) "KE4" (by KetoneAid)
 - Beta-hydroxybutyrate monoester
- 2) "Kenetik" (by DrinkKenetik)
 - Beta-hydroxybutyric acid
- 3) "Ketone 2.0" (by HVMN)
 - 1,3-Butanediol

All participants will provide written informed consent before start of data collection. Following screening and informed consent, eligible participants will participate in three experimental trials of β -OHB supplementation with the order of treatment randomized, balanced, and separated by at least 48 hours. Pre-menopausal women will be tested in the follicular phase (days 3-9) to minimize any potential changes in insulin sensitivity across the menstrual cycle [9]. Participants will be asked to refrain from structured exercise and alcohol on the day before each trial. Furthermore, participants will be instructed to record their dietary intake on the day prior to their first experimental visit, and to consume the same foods and quantities on the days before the subsequent experimental visits. Participants will then be asked to fast overnight (at least 8 hours) and refrain from taking any medications on the morning of the trial.

Upon arrival, a baseline fasting blood sample will be obtained via finger prick. The oral ketone supplement will then be consumed within 5 minutes. The different

supplement types will have an overall similar yet likely distinguishable flavour and will be provided at different volumes (based on the manufacturer's formulation) – however, participants will not be aware which flavour and volume will correspond to which ketone supplement. Furthermore, all supplements will be provided in opaque plastic bottles (labelled with "A", "B", or "C" according to a code that only the principal investigator has access to) such that neither the participant nor the research lead will be able to visually identify the supplement type. Each ketone supplement will be provided at a dose of 10 g active ingredient (i.e., 10 g of betahydroxybutyrate monoester, betahydroxybutyric acid, or 1,3-Butanediol). This is the recommended serving size for the two new ketone supplements to be tested (betahydroxybutyric acid and 1,3-Butanediol) and is in line with a previous pharmacokinetic study that showed a dose of \sim 10 g betahydroxybutyrate monoester to successfully raise β -OHB within 30 minutes [2]. Specifically, this leads to one trial each with:

- 1) 20 mL of "KE4" (i.e.,10 g beta-hydroxybutyrate monoester)
- 2) 237 mL of "Kenetik" (i.e., 10 g beta-hydroxybutyric acid)
- 3) 35 mL of "Ketone 2.0" (i.e., 10 g 1,3-Butanediol)

The primary outcome will be total β -OHB as represented by the area under the curve across 4 hours. Secondary outcomes include blood glucose, blood pressure, heart rate, taste and supplement acceptability, hunger and fullness, and gastrointestinal tolerability - all measured across the 240-minute post-supplementation period. Blood samples will be collected via finger prick; blood β -OHB and glucose levels will be measured using the "Keto-Mojo" handheld monitor at baseline and 15, 30, 60, 90, 120, 180, and 240 minutes after ingestion of the ketone supplement.

Visits Summary

The study will involve a total of 3 visits to the laboratory.

Visit 1: Baseline screening & first experimental trial (duration 270 minutes)

Individuals will be recruited by word-of-mouth. Individuals must be able to read and understand English in order to understand the study instructions. On the initial visit, the potential participant will read through the information and consent form, be able to ask any questions, and provide written informed consent. The research lead ([name] Candidate) will ensure that the participant understands the details of the study and consent form.

Inclusion criteria will be: i) over the age of 18; and ii) able to fast overnight. **Exclusion criteria** will include: i) being a competitive endurance athlete; ii) following a ketogenic diet, low-calorie diet, periodic fasting regimen, or regularly consuming ketogenic supplements; iii) being unable to travel to and from the university; iv) being unable to follow the diet instructions; v) being pregnant or planning to become pregnant during the study; vi) having been diagnosed with a chronic disorder of glucose or fat metabolism, including type 2 diabetes, chronic pancreatitis, or gallbladder disease; vii) being unable to read or communicate in English.

Females will complete the menstrual cycle questionnaire to confirm they are in the follicular phase. Anthropometric and physiologic measurements will be collected (height, body weight, waist circumferences, blood pressure) for baseline participant characterization. The research lead will review the dietary record with the participant and confirm the participant is fasted and has refrained from structured exercise and alcohol the day prior.

A baseline finger prick will then be performed before ingestion of the ketone supplement. Another 7 finger pricks will be performed at 15, 30, 60, 90, 120, 180,

and 240 minutes after ingestion of the supplement. Throughout the 240-minute period, participants will be allowed to do quiet work or perform other sedentary activities (reading, watching a movie). Participants will be asked to complete the questionnaire on gastrointestinal discomfort 60 minutes after ingestion of the supplement, and the questionnaires on hunger and fullness as well as taste and supplement acceptability at the end of the 240-minute post-supplementation period.

At the end of the visit, the participant will be reminded to consume the same diet on the day before the next experimental trial, and to refrain from structured exercise and alcohol consumption in the 24 hours prior.

Visits 2 & 3: Second and third experimental trial (duration 240 minutes)

The second and third experimental trial will be identical to the first visit (except no baseline anthropometric measurements will be performed), with the only difference being the different ketone supplement provided to the participant.

Statistical Analyses

Descriptive statistics (means, SD, and frequencies) will be calculated. Significance will be set at P < 0.05. Data across time will be analyzed in R using a linear mixed effects model with subjects as a random factor and condition and time as fixed factors. Assumptions will be tested using Q-Q plots of residuals. Data with skewed distributions will be log-transformed or non-linear mixed effects models will be used. All participants will be included in the intention-to-treat (ITT) analyses and missing data will not be imputed, per contemporary guidelines with use of linear mixed models [10].

Sample Size

We will recruit 12 participants to be included in this cross-over study, which has blood β-OHB (as represented by the area under the curve across the 4 hours following ingestion of the supplement) as the primary outcome. A previous pharmacokinetic study exploring the effects of a ketone monoester provided at a dose of \sim 10 g in healthy adults found that blood β -OHB was raised to 1.4 \pm 0.6 mM within 30 minutes, and to an average of 0.5 ± 0.5 mM across the entire 4-hour post-supplementation period [2], which represents an effect size of d > 1.0compared to baseline. Using the outcome data from this study (N = 15) and assuming 80% power with an alpha level of 0.05 and a moderate correlation between repeated measures of 0.5, a total sample size of N = 6 would be sufficient to detect an increase in average blood β-OHB compared to baseline (calculated using G*Power v3.1). In order to allow for a more nuanced evaluation of differences between ketone supplements and to account for any dropouts or missing blood samples, we will recruit 12 participants (aiming for equal males and females), which is in line with the sample size of previous pharmacokinetic studies of ketone supplements [2].

Significance

The results of this study will help determine the effect of different types of ketone supplements on blood β -OHB and glucose. This is a pilot study and it will provide useful data to better answer future research questions and aid in the design of longer-term studies.

Outcome Measurements and Methods

The primary outcome will be total β -OHB as represented by the area under the curve across 4 hours. Secondary outcomes include blood glucose, blood pressure, heart rate, hunger and fullness, gastrointestinal discomfort, and taste and supplement acceptability.

Anthropometric Measures

Waist circumference (cm), height (cm), and weight (kg) will be measured using standard procedures. Body mass index (BMI) will be calculated as kg/m².

Physiological Measures

Resting blood pressure and heart rate will be collected for descriptive purpose and throughout the study visits (at the same time points as blood samples are collected). Before measurements, participants will be instructed to sit quietly and rest for 5 minutes. A finger tip heart rate monitor will track heart rate. Blood pressure will be collected using a cuff around the upper arm, a stethoscope will be placed in the cubital fossa for systolic and diastolic blood pressure.

Blood Sampling

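### Minor safety point: participants are asked to skip all medication on three trial mornings, with no stated exception for essential drugs and no described check of what was taken

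*Combined protocol and SAP*

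**What the plan says.** Experimental design sets the rule for each trial: "Participants will then be asked to fast overnight (at least 8 hours) and refrain from taking any medications on the morning of the trial". Each participant has three trials, at least 48 hours apart.

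Under Visits Summary, Visit 1, the inclusion criteria are "i) over the age of 18; and ii) able to fast overnight". The one exclusion that names diagnosed disease is "having been diagnosed with a chronic disorder of glucose or fat metabolism, including type 2 diabetes, chronic pancreatitis, or gallbladder disease". The other exclusions concern endurance sport, diet and ketogenic supplements, travel, diet instructions, pregnancy and English. None concerns medication.

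Visit 1 is headed "Baseline screening & first experimental trial (duration 270 minutes", and consent belongs to it: "On the initial visit, the potential participant will read through the information and consent form". Blood pressure is among the measurements taken that day: "physiologic measurements will be collected (height, body weight, waist circumferences, blood pressure) for baseline participant characterization". No cut-off is attached.

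Before dosing, the research lead reviews the dietary record and must "confirm the participant is fasted and has refrained from structured exercise and alcohol the day prior". For the later visits, "The second and third experimental trial will be identical to the first visit", apart from the anthropometric measurements. The reminder at the end of Visit 1 covers diet, exercise and alcohol.

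Objective (c) compares blood pressure and heart rate across the supplements. Physiological Measures schedules both at the same times as the blood samples.

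**The concern.** The rule covers every drug. The plan describes its participants as healthy adults, but the listed criteria do not turn that label into a screen for treated hypertension, asthma, epilepsy, thyroid disease or any other condition that may need a morning dose. Someone with such a condition who follows the request literally leaves out or delays an essential drug on three days. On the first of those days this happens before any screening that the plan describes.

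The data issue is smaller. Drug intake could affect blood pressure and heart rate, which are secondary outcomes. If a participant takes a drug before one visit and not before another, the difference falls on one supplement and not the others. The plan verifies fasting, exercise and alcohol to prevent this kind of inconsistency, but it describes no such step for medication.

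**Working it through.** The plan gives no figure on this point to reproduce. The check is mainly a reading of the sections against each other, with simple arithmetic to show scale.

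**1. Is there an exception?** None appears in the supplied text.

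**2. Would eligibility remove people who need a morning drug?** Not through the listed items. Age has no upper limit, the disease exclusion is confined to glucose and fat metabolism, and Visit 1 blood pressure is descriptive only.

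**3. When does screening happen relative to the first omitted dose?** Consent and screening are placed within Visit 1, which is also the first trial. The medication request applies to that same morning, so it takes effect first.

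**4. Is medication checked?**

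| Step | Covers | Medication |
|---|---|---|
| Check before dosing, Visit 1 | dietary record, fasting, exercise, alcohol | not mentioned |
| Reminder at the end of Visit 1 | diet, exercise, alcohol | not mentioned |
| Visits 2 and 3 | as Visit 1 | not mentioned |

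The reminder also leaves out the fast, so its silence on medication is weaker evidence than the silence of the check.

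**5. Illustrative delay.** Inputs are the visit durations, 270 minutes for Visit 1 and 240 minutes for Visits 2 and 3. The assumption is a dose due at arrival and taken when the visit ends.
- Visit 1: 270 / 60 = 4.5 hours.
- Visits 2 and 3: 240 / 60 = 4.0 hours each.

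A dose due earlier that morning is delayed longer. An evening dose is not delayed.

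**6. Closest spacing.** With the minimum gap of 48 hours (2 days), the trials fall on day 1, day 1 + 2 = 3 and day 3 + 2 = 5. That makes 3 of 5 consecutive mornings. Wider spacing lowers this share.

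**7. Readings affected if one participant's medication differs at one visit.** There are 8 time points per visit (baseline, 15, 30, 60, 90, 120, 180 and 240 minutes), 3 visits and 12 participants.
- Within that person: 8 / (8 × 3) = 8/24 = 33%, all under one supplement.
- Within that supplement condition: 8 / (8 × 12) = 8/96 = 8.3%.
- Across the trial: 8 / (24 × 12) = 8/288 = 2.8%.

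These are counts of time points for each measure. They do not give the size of any shift.

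**The case against.** The strongest reply is that the safety issue needs a participant whom the documents do not show. The trial enrols 12 healthy adults, metabolic disease is excluded, and the exclusions are introduced as including the listed items, so the list may not be closed. Participants are asked to abstain for a morning at a time, and nothing tells them to stop treatment. An exception, or advice to mention regular drugs, could well sit in the information and consent form, which is not in our copy. All of this stands, and it keeps the point minor.

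The order of events is also less than fully clear. Experimental design speaks of eligible participants entering the trials after screening and consent. The diet record and fast before Visit 1 imply earlier contact, at which someone might ask about medication. That is fair, but no such question is described, and the Visit 1 section places both screening and consent on the day of the first trial.

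The two harms also arise under opposite conditions. The delay occurs when the participant complies. The inconsistency occurs when medication differs between visits. If the drug is omitted at all three visits, the within-person comparisons are largely intact. A uniform omission is a reasonable way to standardise a fasted comparison, and that supports keeping the rule for drugs that can safely wait.

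A reader might infer that the supplement comparisons are biased, that the primary AUC is compromised, or that participants will be put at serious risk. The documents support none of these. Nothing links this rule to the beta-OHB AUC, no difference in medication between visits is shown, and neither the likelihood nor the size of an effect can be derived. Nor do the documents show that people on regular medication have to be excluded.

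**Conclusion.** The point holds as a minor one. A stated rule, followed literally, would have a participant omit or delay an essential drug on three mornings, the first of them before any described screening. The described steps would also not reveal a difference in medication between visits. Only the secondary blood pressure and heart rate comparisons could be touched.

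The delay of about 4 to 4.5 hours describes a hypothetical person with a dose due at arrival. The figure of 3 in 5 mornings assumes minimum spacing throughout. The conclusion rests on the supplied text alone. If the consent form already contains an exception or a medication question, what remains is to bring the protocol into line with it.

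**What to change.** Make three small changes.

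1. Reword the instruction so that it covers only non-essential medication.
2. Ask about regular medication when the pre-visit instructions for Visit 1 are given. A question asked at Visit 1 itself comes after the dose has been left out.
3. Add medication taken or omitted that morning to the existing check at every visit, and keep it the same, including timing, across a participant's three visits.

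No new exclusion rule is needed. The cost is one reworded sentence, one question and one checklist item. The small downside is that a participant who continues a drug may add some variability to blood pressure and heart rate. The record from step 3 would at least make that visible.

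### Gastrointestinal discomfort is recorded once, at 60 minutes, so no scheduled form described in the plan can record symptoms that begin later in the 240-minute visit

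*Combined protocol and SAP*

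**What the plan says.** Objective (d) reads: "To investigate the effect of acute supplementation with different ketone supplements on gastrointestinal discomfort, hunger, and fullness". In Experimental design, the sentence on secondary outcomes names six items and ends with "hunger and fullness, and gastrointestinal tolerability - all measured across the 240-minute post-supplementation period".

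The times are set under Visits Summary, Visit 1. Participants are to "complete the questionnaire on gastrointestinal discomfort 60 minutes after ingestion of the supplement", and they complete "the questionnaires on hunger and fullness as well as taste and supplement acceptability at the end of the 240-minute post-supplementation period". The heading for visits 2 and 3 says: "The second and third experimental trial will be identical to the first visit", apart from the anthropometric measurements and the product given.

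Outcome Measurements and Methods lists gastrointestinal discomfort as a secondary outcome but gives no further times. By contrast, blood samples, blood pressure and heart rate are taken at baseline and at 15, 30, 60, 90, 120, 180 and 240 minutes.

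**The concern.** The outcome description covers the full 240 minutes, but the only gastrointestinal form is completed a quarter of the way through. Whatever its wording or recall period, a form filled in at 60 minutes cannot describe what happens afterwards.

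Tolerability is part of the motivation for studying these products. The Background acknowledges it in the clause beginning "While qualities such as an improved taste and gastrointestinal tolerability are desirable in ketone supplements", and it reports that ketone salts upset the gut in many people. It also says that the kinetics of the two newer products are poorly known. The early rise in blood β-OHB, which might support an early form, is cited for the monoester only (Experimental design and Sample Size). If symptoms come on at different times with different products, a single early form favours the product with the later onset. The pilot is meant to inform longer studies, so its tolerability result should at least be labelled with the period it covers.

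**Working it through.** The plan states no figure for this point, so there is none to reproduce. The check compares the schedule with the outcome description.

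**Inputs**
- Post-dose period: 240 minutes (Experimental design).
- Gastrointestinal form: once, at 60 minutes (Visits Summary, Visit 1); the same at visits 2 and 3.
- Post-dose contact times: 15, 30, 60, 90, 120, 180 and 240 minutes, which is 7 (Experimental design; Physiological Measures).
- Forms already completed at the end of the 240 minutes: hunger and fullness, taste and acceptability.
- Participants: 12; visits: 3.

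**Time after the only form**
- 240 − 60 = 180 minutes; 180 / 240 = 75%.
- Contact times after 60 minutes: 90, 120, 180 and 240, so 4 of 7.

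**Effect on the comparison**

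For a given supplement, let p be the proportion of participants with any symptom in the 240 minutes, and let q be the share of those whose symptoms all begin after 60 minutes. At best, the form detects p × (1 − q).
- If q is the same for supplements A and B, the observed difference is (p_A − p_B) × (1 − q): the direction is right, but the difference is too small.
- If A and B are equally tolerated (p_A = p_B = p) but differ in onset, the observed difference A minus B is p × (q_B − q_A). This is not zero, and it favours the supplement with the later onset.

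The documents give neither p nor q for any of the three products, so the bias cannot be sized. The 75% is a share of clock time, not of symptoms missed.

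**Burden of a second form**
- 1 form × 3 visits = 3 per participant; 3 × 12 = 36 in total.
- At an assumed 1 to 2 minutes per form, this is 3 to 6 minutes per participant over the whole study.

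**The case against.** The strongest reply is that there is no real contradiction. Taste and acceptability appear in the same list of outcomes and are also rated once, so the sentence may mean only that each outcome is assessed at some point within the 240 minutes. The visit schedule is specific, and staff would know what to do. This stands: the wording alone does not prove a conflict. It does not answer the narrower point, because on either reading nothing described records symptoms that begin after 60 minutes.

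It can also be said that an early form is reasonable for the monoester, that the Background does not link blood kinetics to the timing of gut symptoms, and that late symptoms might be picked up by the acceptability form or by spontaneous report. The first two are fair and are why the size is left open. The third cannot be excluded, since the questionnaires are not reproduced and some pages were removed, but no such recording is described.

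Two stronger readings are tempting and are not supported:
- **Hunger and fullness are also mistimed.** The 240-minute rating gives a fair comparison between supplements: order is randomized, and fasting and prior-day diet are standardized. Objective (d) promises no time course for appetite.
- **The analysis model fails because time would have one level.** The plan confines the "linear mixed effects model with subjects as a random factor and condition and time as fixed factors" to data across time and separately provides for descriptive statistics. Nothing assigns single ratings to a model with a time factor.

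**Conclusion.** The point holds for gastrointestinal discomfort only. As planned, the outcome covers at most the first 60 of the 240 minutes, and the comparison between supplements could be distorted if onset differs between products.

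A reader might infer that tolerability results will be wrong, or that some number of the 12 participants will be misclassified. The documents do not support that: they contain no incidence or onset data, and any such count would be invented.

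The conclusion assumes that no other gastrointestinal or adverse-event recording takes place after 60 minutes; none is described. It does not depend on the form's recall period. Severity is low: this is a change the team could make, on a secondary outcome in an exploratory pilot. The β-OHB primary outcome and the sample size are untouched.

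**What to change.** Repeat the gastrointestinal discomfort questionnaire at 240 minutes, alongside the forms already completed then, at all three visits. Word its instruction to cover the period since the 60-minute form; asking only about the present moment would miss symptoms that come and go in between. State the recall period of the 60-minute form as well. Compare supplements within subject on the 60-minute and the 240-minute forms, reporting both.

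If the second form is not added, report the result as symptoms up to 60 minutes only, and align the outcome sentence in Experimental design with the times in the visit schedule.

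The cost is one short extra form per visit (36 in total) and a small amendment, with no new visit, contact time or staff. The listing "Second and third experimental trial (duration 240 minutes" already equals the post-dose period, so the added minute or two falls at the end with the other forms. Hunger, fullness and taste timing need no change.

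### Taste is rated only once, about four hours after the drink, so the rating is recalled and may be coloured by after-effects that differ by product

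*Combined protocol and SAP*

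**What the plan says.** Objective (e) reads "To explore supplement acceptability and taste across different ketone supplements". Taste and acceptability are also listed as secondary outcomes, both under Experimental design and under Outcome Measurements and Methods.

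On exposure, Experimental design states: "The oral ketone supplement will then be consumed within 5 minutes".

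On timing, only the Visit 1 description in the Visits Summary gives questionnaire times. The first is early: "Participants will be asked to complete the questionnaire on gastrointestinal discomfort 60 minutes after ingestion of the supplement". The others come last: participants complete "the questionnaires on hunger and fullness as well as taste and supplement acceptability at the end of the 240-minute post-supplementation period". The text on visits 2 and 3 then says: "The second and third experimental trial will be identical to the first visit". The exceptions it makes are the baseline anthropometry and the supplement given.

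Just before the Visits Summary, the secondary outcomes, taste among them, are described as "all measured across the 240-minute post-supplementation period". That sentence gives no time points for taste.

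The Background explains why taste is of interest. It says that "ketone monoesters have an extremely unpleasant bitter taste", and it introduces the two newer products as offering a better consumer experience.

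**The concern.** Taste is perceived while drinking. A rating taken some four hours later is a memory of it. By then the participant has had whatever gastrointestinal effects the product produces and has already answered a questionnaire directing attention to them. Any bitterness has also had time to fade. The Background treats taste and gastrointestinal tolerability as two separate properties of a supplement, but a single late rating cannot cleanly separate them. A difference in taste score between two products could reflect the taste, a later stomach upset, or how quickly the taste was forgotten.

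Randomised, balanced order protects against period effects. It does not protect against an after-effect caused by the product itself, because that follows the product into every sequence and stays in the between-product contrast.

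At stake is how the taste half of objective (e) is interpreted. The pilot is meant to inform longer studies, and the Background links taste to adherence. An immediate taste impression that was not recorded at the visit cannot be recovered by analysis.

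**Working it through.** The plan gives no figure to reproduce here and no rating-scale data, so the check is of intervals and of what the schedule does and does not contain.

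**Inputs**
- Drinking time: at most 5 minutes (Experimental design).
- Gastrointestinal questionnaire: 60 minutes (Visit 1).
- Taste and acceptability questionnaire: 240 minutes (Visit 1).
- First post-dose sample: 15 minutes, with blood pressure and heart rate at the same time points after 5 minutes of seated rest (Physiological Measures).
- Participants and visits: 12 and 3.

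**Delay from tasting to rating**
- Clock started when drinking begins: 240 − 5 = 235 minutes, or 3.9 hours, after the latest permitted finish.
- Clock started when drinking ends: 240 minutes, or 4.0 hours.
- Interval between the gastrointestinal and taste questionnaires: 240 − 60 = 180 minutes.
- Ratings with this delay: 12 x 3 = 36, which is all of them.

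**Is there an earlier taste rating elsewhere?** No. The general sentence on secondary outcomes speaks of the whole 240-minute period, while the Visit 1 schedule fixes one time at its end. The general sentence supplies no earlier rating. The two statements do not match and should be aligned.

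**What could differ between products?**
- Gastrointestinal after-effects: possible. The servings differ in volume (20, 237 and 35 mL) and in active ingredient, so equal after-effects cannot be assumed. No figures for these three products are given.
- Fading of the taste: possible for the same reasons, and likewise without data.
- Hunger from fasting: at least 8 hours overnight plus 4 hours at the visit gives at least 12 hours, assuming no meal is served, since none is described. This applies equally at all three visits, so it is not in itself a between-product bias.

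**Does an immediate rating fit before the 15-minute sample?** Take the tighter case, with the clock started when drinking begins, and assume 1 minute for the form: 5 + 1 + 5 = 11 minutes. The form could take up to 15 − 5 − 5 = 5 minutes and still fit.

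**The case against.** The strongest reply is that bias is not demonstrated. The Background attributes gastrointestinal discomfort to ketone salts, and no salt is tested. The two mechanisms, stomach upset lowering a score and fading bitterness softening one, could act on different products or offset each other. The questionnaire wording is not in the documents, so its items may ask specifically about taste while drinking, and a recalled answer can still be about taste. Gastrointestinal discomfort is recorded separately at 60 minutes and can be read alongside the taste scores. Taste is also a minor outcome: the last-listed objective, worded as exploration, in a descriptive pilot whose stated aim concerns β-OHB and glucose.

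Most of this stands, and it limits the point. A reader might infer that a product which upsets the stomach will be marked down on taste, or that the taste comparison is biased. The documents support only that it may be. A reader might also infer that the whole of objective (e) is compromised. It is not: overall acceptability can properly include after-effects, so a late rating suits that half.

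The reply does not remove the delay. The separate 60-minute score makes contamination partly open to inspection but does not correct it, and it says nothing about the three hours that follow.

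**Conclusion.** The point holds for taste only. All 36 planned taste ratings are recalled ones, given about 235 to 240 minutes after the drink. They may be influenced by after-effects or fading that could vary by product and that balanced order would not remove. Confidence is high on the schedule. On the consequence, the documents allow no estimate of direction or size. The conclusion assumes that the Visit 1 schedule is the operative one and that the questionnaire contains items on taste as experienced while drinking.

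The scope is one secondary, exploratory outcome. The primary area under the curve and the sample-size reasoning are untouched. The change is worth making because it is cheap and the information cannot be recovered later, not because an error in the results has been shown.

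**What to change.** In the Visit 1 schedule, which visits 2 and 3 inherit:

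- Have participants complete the taste items immediately after finishing the supplement and before the 15-minute sample. Name that rating as the taste outcome for objective (e).
- Keep overall supplement acceptability at 240 minutes, where after-effects belong.
- If the taste and acceptability items cannot be separated, give the whole questionnaire at both times.
- Reword the general statement on secondary outcomes under Experimental design so that it agrees with this schedule.

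The cost is one or two sentences of text and about a minute of form-filling (assumed) before the 15-minute finger prick; giving the whole questionnaire twice would add one extra form per visit. No visit, staff or procedure is added.
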